**Table 2. Stage 1 Study Design**

		Vaccination 1	Post– Vaccination 1 Blood Draw	Vaccination 2	Post– Vaccination 2 Blood Draw	Safety Telephone Call	Telephone Call
	Approximate Month	0	1	6	7	12	
	Visit Number	1	2	3	4	5	6
ACWY-Naïve Subjects	Group 1 a (n=265)	MenABCWY + saline		MenABCWY			
	Group 2 (n=530)	Bivalent rLP2086 + MenACWY-CRM		Bivalent rLP2086			
	Blood draw for serum collection	20 mL (or up to 100 mL in subset)	20 mL (or up to 100 mL in subset)	20 mL	20 mL (or up to 100 mL in subset)		
ACWY- Experienced Subjects	Group 3 a (n=265)	MenABCWY + saline		MenABCWY			
	Group 4 (n=530)	Bivalent rLP2086 + MenACWY-CRM		Bivalent rLP2086			
	Blood draw for serum collection	20 mL (or up to 100 mL in subset)	20 mL (or up to 100 mL in subset)	20 mL	20 mL (or up to 100 mL in subset)		
Subjects 18 to 25 Years of Age (Naïve or Experienced)	Optional blood draw for whole blood collection				50 mL		

a. Pilot cohort subjects will be assigned to either Group 1 or 3, but will receive only MenABCWY and not saline at Vaccination 1.

**Table 3. Stage 2 Study Design**

		Antibody Persistence	Booster Vaccination	Postbooster Blood Draw	Safety Telephone Call
	Approximate Month	18-42	54	55	60
	Visit Number	7-9	10	11	12
ACWY-Naïve Subjects	Group 1 (n~132)		MenABCWY		
	Group 2 (n~65)		Bivalent rLP2086 + MenACWY-CRM		
ACWY-Experienced Subjects	Group 3 (n~132)		MenABCWY		
	Group 4 (n~65)		Bivalent rLP2086 + MenACWY-CRM		
	Blood draw for serum collection	20 mL × 3	20 mL	20 mL (or up to 100 mL in subset)	

### 2.2.3. Schedule of Activities

The Schedule of Activities table provides an overview of the protocol visits and procedures. Refer to the Study Procedures and Assessments sections of the protocol for detailed information on each procedure and assessment required for compliance with the protocol.

The investigator may schedule visits (unplanned visits) in addition to those listed on the Schedule of Activities table in order to conduct evaluations or assessments required to protect the well-being of the subjects.

**Table 4. Schedule of Activities**

Stage 1						
Visit ID	Visit 1	Visit 2	Visit 3	Visit 4	Visit 5	Visit 6
Visit Description	Vaccination 1	Post– Vaccination 1 Blood Draw	Vaccination 2	Post– Vaccination 2 Blood Draw	Telephone Contact	Telephone Contact
Approximate Month	0	1	6	7	6 Months After Last Study Vaccination	
Visit Window	Day 1	28 to 42 Days After Visit 1	173 to 194 Days After Visit 1	28 to 42 Days After Visit 3	168 to 196 Days After Visit 3	After Study Unblinding and Before Transition to Stage 2 a
Informed consent	X					
Informed consent for optional blood draw for whole blood collection b				X		
Review eligibility criteria	X					
Demography	X					
Confirm continued eligibility c		X	X	X		
Medical history and physical examination	X					
Record previous PRP-OMP vaccinations	X					
Record any previous meningococcal vaccinations	X					

**Table 4. Schedule of Activities**

Stage 1						
Visit ID	Visit 1	Visit 2	Visit 3	Visit 4	Visit 5	Visit 6
Visit Description	Vaccination 1	Post– Vaccination 1 Blood Draw	Vaccination 2	Post– Vaccination 2 Blood Draw	Telephone Contact	Telephone Contact
Approximate Month	0	1	6	7	6 Months After Last Study Vaccination	
Visit Window	Day 1	28 to 42 Days After Visit 1	173 to 194 Days After Visit 1	28 to 42 Days After Visit 3	168 to 196 Days After Visit 3	After Study Unblinding and Before Transition to Stage 2a
Record use of antipyretics and other pain medications received on the day prior to vaccination	X		X			
Urine pregnancy test for female subjects	X		X			
Oral temperature	X		X			
Randomization	X					
Obtain blood sample(s) for serum collection d	20 mL (up to 100 mL in subset)	20 mL (up to 100 mL in subset)	20 mL (20 mL in subset)	20 mL (up to 100 mL in subset)		
Additional optional blood draw for whole blood collection e				50 mL		
Investigational product administration and observation f	X		X			
Record nonstudy vaccinations		X	X	X	X	
Provide subject with an e-diary, caliper, measuring tape/ruler, and thermometer, if necessary	X		X			
Review and collect e-diary		X		X		
Assess reactogenicity and record use of antipyretic medication g	Days 1 to 7		Days 1 to 7			
Provide the subject with a contact card	X					
Provide the subject with a memory aid				X		
Complete Study Visit/Telephone Contact AE Checklist h		X	X	X	X	

**Table 4. Schedule of Activities**

Stage 1						
Visit ID	Visit 1	Visit 2	Visit 3	Visit 4	Visit 5	Visit 6
Visit Description	Vaccination 1	Post-Vaccination 1 Blood Draw	Vaccination 2	Post-Vaccination 2 Blood Draw	Telephone Contact	Telephone Contact
Approximate Month	0	1	6	7	6 Months After Last Study Vaccination	
Visit Window	Day 1	28 to 42 Days After Visit 1	173 to 194 Days After Visit 1	28 to 42 Days After Visit 3	168 to 196 Days After Visit 3	After Study Unblinding and Before Transition to Stage 2 a
Record concomitant medications used to treat AEs	X	X	X	X	X	
(S)AE collection appropriate for the visit i	X	X	X	X	X	
Notification of Stage 2 participation						X

Abbreviations: e-diary = electronic diary; PRP-OMP = polyribosylribitol phosphate oligosaccharide of *Haemophilus influenzae* type b conjugated to outer membrane protein.

- a. Visit 6 must be conducted prior to Visit 7.
- b. Applicable only at designated sites. This consent relating to the whole blood sample may be obtained at prior visits if appropriate.
- c. Ensure that the subject continues to be eligible for the study and continues to comply with contraception requirements, as appropriate.
- d. Subject participation in the subset will be voluntary for subjects 18 to 25 years of age, and the volume of blood drawn (either 50 mL or 100 mL) will depend on the consent obtained.
- e. Applicable only for subjects at designated sites who have given consent for this additional blood draw.
- f. Observe the subject for at least 30 minutes (or longer as per local practice) after the investigational product administration for any acute reactions.
- g. Between visits, review the e-diary data online at frequent intervals. Contact the subject in order to obtain stop dates for any local reactions, systemic events, or use of antipyretic medication that was ongoing on the last day that the e-diary was completed.
- h. Checklist includes questions regarding newly diagnosed chronic medical conditions, medically attended adverse events, and missed days of school or work, as well as about neuroinflammatory and autoimmune conditions, such as transverse myelitis, uveitis, optic neuritis, and multiple sclerosis.
- i. Please refer to protocol Section 8.1.4.

Stage 2						
Visit ID	Visit 7	Visit 8	Visit 9	Visit 10	Visit 11	Visit 12
Visit Description	Antibody Persistence Blood Draw 1	Antibody Persistence Blood Draw 2	Antibody Persistence Blood Draw 3	Booster Vaccination	Postbooster Blood Draw	Telephone Contact
Approximate Month	18	30	42	54	55	6 Months After Booster Vaccination
Visit Window	336 to 694 Days After Visit 3	700 to 756 Days After Visit 3a	1064 to 1120 Days After Visit 3	1428 to 1484 Days After Visit 3	28 to 42 Days After Visit 10	168 to 196 Days After Visit 10
Informed consent	X					
Confirm continued eligibility b	X	X	X	X	X	
New medical history and physical examination				X		
Urine pregnancy test for female subjects				X		
Oral temperature				X		
Obtain blood sample	20 mL	20 mL	20 mL	20 mL	20 mL (up to 100 mL in subset)	
Record use of antipyretics and other pain medications received on the day prior to vaccination				X		
Investigational product administration and observation c				X		
Record nonstudy vaccinations	X	X	X	X	X	
Provide subject with an e-diary, caliper, measuring tape/ruler, and thermometer, if necessary				X		
Review and collect e-diary					X	
Assess reactogenicity and record use of antipyretic medication d				Day 1 to 7		
Provide the subject with a memory aid					X	
Complete Study Visit/Telephone Contact AE Checklist e					X	X

Stage 2						
Visit ID	Visit 7	Visit 8	Visit 9	Visit 10	Visit 11	Visit 12
Visit Description	Antibody Persistence Blood Draw 1	Antibody Persistence Blood Draw 2	Antibody Persistence Blood Draw 3	Booster Vaccination	Postbooster Blood Draw	Telephone Contact
Approximate Month	18	30	42	54	55	6 Months After Booster Vaccination
Visit Window	336 to 694 Days After Visit 3	700 to 756 Days After Visit 3a	1064 to 1120 Days After Visit 3	1428 to 1484 Days After Visit 3	28 to 42 Days After Visit 10	168 to 196 Days After Visit 10
Record concomitant medications used to treat AEs	X	X	X	X	X	X
(S)AE collection appropriate for the visit f	X	X	X	X	X	X

Abbreviation: e-diary = electronic diary.

- a. Visit 7 and Visit 8 should be conducted within no less than 30 days of each other. If Visit 7 cannot be conducted within the protocol-defined visit window, Visit 7 can be omitted and Visit 8 performed directly.
- b. Ensure that the subject continues to be eligible for the study and continues to comply with contraception requirements, as appropriate.
- c. Observe the subject for at least 30 minutes (or longer as per local practice) after the investigational product administration for any acute reactions.
- d. Between visits, review the e-diary data online at frequent intervals. Contact the subject in order to obtain stop dates for any local reactions, systemic events, or use of antipyretic medication that was ongoing on the last day that the e-diary was completed.
- e. Checklist includes questions regarding newly diagnosed chronic medical conditions, medically attended adverse events, and missed days of school or work, as well as about neuroinflammatory and autoimmune conditions, such as transverse myelitis, uveitis, optic neuritis, and multiple sclerosis.
- f. Please refer to protocol Section 8.1.4.

### **3. ENDPOINTS AND BASELINE VARIABLES: DEFINITIONS AND CONVENTIONS**

#### **3.1. Primary Endpoints**

##### **3.1.1. Primary Immunogenicity Endpoints**

Five coprimary endpoints are defined for the primary objectives; they are defined for hSBA performed with each of the 4 primary test strains: PMB80 (A22), PMB2001 (A56), PMB2948 (B24), and PMB2707 (B44).

- One of the 5 coprimary endpoints is the composite endpoint defined as the proportion of subjects achieving an hSBA titer  $\geq$  lower limit of quantitation (LLOQ: 1:16 for A22 and 1:8 for A56, B24, and B44) for all 4 primary test strains combined, 1 month after the second vaccination (Visit 4) in the bivalent rLP2086 arms (Group 2 and 4 subjects) combined.
- Four of the coprimary endpoints are defined as the proportion of subjects achieving at least a 4-fold increase in hSBA titer from baseline to 1 month after the second vaccination (Visit 4) in the bivalent rLP2086 arms (Group 2 and 4 subjects) combined for each of the 4 primary test strains.
  - For subjects with a baseline hSBA titer below the limit of detection (LOD, or an hSBA titer of  $<1:4$ ), a 4-fold response is defined as an hSBA titer of  $\geq 1:16$  or the LLOQ (whichever titer is higher).
  - For subjects with a baseline hSBA titer of  $\geq$  LOD (ie, hSBA titer of  $\geq 1:4$ ) and  $<$  LLOQ, a 4-fold response is defined as an hSBA titer of  $\geq 4$  times the LLOQ.
  - For subjects with a baseline hSBA of  $\geq$  LLOQ, a 4-fold response is defined as an hSBA titer of  $\geq 4$  times the baseline titer.

##### **3.1.2. Primary Safety Endpoints**

The following endpoints will be described after Vaccinations 1 and 2 in the bivalent rLP2086 arms (Group 2 and 4 subjects) combined.

- Percentage of subjects reporting local reactions (pain, redness, and swelling) and by severity within 7 days after each vaccination visit.
- Percentage of subjects reporting systemic events (fever, vomiting, diarrhea, headache, fatigue, chills, muscle pain other than muscle pain at any injection site, and joint pain) and by severity within 7 days after each vaccination visit.
- Percentage of subjects reporting the use of antipyretic medications within 7 days after each vaccination visit.

- Percentage of subjects with at least 1 SAE during the following time periods:
  - 30 Days after each vaccination
  - 30 Days after any vaccination
  - During the Stage 1 vaccination phase (from the first study vaccination [Visit 1] through 1 month after the second study vaccination [Visit 4])
  - During the Stage 1 follow-up phase (from 1 month after the second study vaccination [Visit 4] through 6 months after the second study vaccination [Visit 5])
  - Throughout Stage 1 (from the first study vaccination [Visit 1] through 6 months after the second study vaccination [Visit 5])
  
- Percentage of subjects with at least 1 MAE occurring during the following time periods:
  - 30 Days after each vaccination
  - 30 Days after any vaccination
  - During the Stage 1 vaccination phase (from the first study vaccination [Visit 1] through 1 month after the second study vaccination [Visit 4])
  - During the Stage 1 follow-up phase (from 1 month after the second study vaccination [Visit 4] through 6 months after the second study vaccination [Visit 5])
  - Throughout Stage 1 (from the first study vaccination [Visit 1] through 6 months after the second study vaccination [Visit 5])
  
- Percentage of subjects with at least 1 NDCMC occurring during the following time periods:
  - 30 Days after each vaccination
  - 30 Days after any vaccination
  - During the Stage 1 vaccination phase (from the first study vaccination [Visit 1] through 1 month after the second study vaccination [Visit 4])
  - During the Stage 1 follow-up phase (from 1 month after the second study vaccination [Visit 4] through 6 months after the second study vaccination [Visit 5])
  - Throughout Stage 1 (from the first study vaccination [Visit 1] through 6 months after the second study vaccination [Visit 5])

- Percentage of subjects with at least 1 AE occurring during the following time periods:
  - 30 Days after each vaccination
  - 30 Days after any vaccination
  - During the Stage 1 vaccination phase (from the first study vaccination [Visit 1] through 1 month after the second study vaccination [Visit 4])
- Percentage of subjects reporting at least 1 immediate AE after each vaccination.
- The number of days subjects missed school or work because of AEs during the Stage 1 vaccination phase (Visit 1 through Visit 4).

The following endpoints will be described after the booster vaccination in Groups 1 through 4:

- Percentage of subjects reporting local reactions (pain, redness, and swelling) and by severity within 7 days after the booster vaccination.
- Percentage of subjects reporting systemic events (fever, vomiting, diarrhea, headache, fatigue, chills, muscle pain other than muscle pain at any injection site, and joint pain) and by severity within 7 days after the booster vaccination.
- Percentage of subjects reporting the use of antipyretic medication within 7 days after the booster vaccination.
- Percentage of subjects with at least 1 SAE during the following time periods:
  - During the booster vaccination phase (from the booster vaccination [Visit 10] through 1 month after the booster vaccination [Visit 11])
  - During the booster follow-up phase (from 1 month after the booster vaccination [Visit 11] through 6 months after the booster vaccination [Visit 12])
  - From the booster vaccination (Visit 10) through 6 months after the booster vaccination (Visit 12)
- Percentage of subjects with at least 1 MAE occurring during the following time periods:
  - During the booster vaccination phase (from the booster vaccination [Visit 10] through 1 month after the booster vaccination [Visit 11])
  - During the booster follow-up phase (from 1 month after the booster vaccination [Visit 11] through 6 months after the booster vaccination [Visit 12])

- From the booster vaccination (Visit 10) through 6 months after the booster vaccination (Visit 12)
- Percentage of subjects with at least 1 NDCMC occurring during the following time periods:
  - During the booster vaccination phase (from the booster vaccination [Visit 10] through 1 month after the booster vaccination [Visit 11])
  - During the booster follow-up phase (from 1 month after the booster vaccination [Visit 11] through 6 months after the booster vaccination [Visit 12])
  - From the booster vaccination (Visit 10) through 6 months after the booster vaccination (Visit 12)
- Percentage of subjects with at least 1 AE occurring during the following time periods:
  - During the booster vaccination phase (from the booster vaccination [Visit 10] through 1 month after the booster vaccination [Visit 11]).
- Percentage of subjects reporting at least 1 immediate AE after the booster vaccination.
- The number of days subjects missed school or work because of AEs after the booster vaccination.

### **3.2. Secondary Endpoints**

#### **3.2.1. Secondary Immunogenicity Endpoints**

Immune response induced by 2 doses of bivalent rLP2086 arms (Group 2 and 4 subjects) combined as measured by 4 primary MenB test strains (A22, A56, B24, and B44) and by secondary MenB test strains: PMB3175 (A29), PMB3010 (A06), PMB824 (A12), PMB3040 (A07), PMB1672 (A15), PMB1989 (A19), PMB648 (B16), PMB866 (B09), PMB1256 (B03), and PMB431 (B15).

- Proportions of subjects with hSBA titers  $\geq$  LLOQ,  $\geq 1:4$ ,  $\geq 1:8$ ,  $\geq 1:16$ ,  $\geq 1:32$ ,  $\geq 1:64$ , and  $\geq 1:128$  for each of the 4 primary MenB test strains at Visit 4.
- hSBA geometric mean titers (GMTs) for each of the 4 primary MenB test strains at Visit 4.
- Proportions of subjects with hSBA titers  $\geq$  LLOQ (1:16 for A06, A19, and A12 and 1:8 for A07, A15, A29, B03, B09, B15, and B16) for each of the secondary MenB test strains 1 month after the second vaccination (Visit 4).
- Proportions of subjects with hSBA titers  $\geq 1:4$ ,  $\geq 1:8$ ,  $\geq 1:16$ ,  $\geq 1:32$ ,  $\geq 1:64$ , and  $\geq 1:128$  for each of the secondary MenB test strains 1 month after the second vaccination (Visit 4).

- hSBA GMTs for each of the secondary test strains 1 month after the second vaccination (Visit 4).

Immune response induced by 1 dose of MenABCWY compared to 1 dose of MenACWY-CRM arms in ACWY-naïve and ACWY-experienced subjects separately.

- Proportion of subjects with hSBA-MenA, hSBA-MenC, hSBA-MenW, and hSBA-MenY titers  $\geq 1:8$  (or LLOQ, whichever is higher) at Visit 2.
- Proportion of subjects with hSBA-MenA, hSBA-MenC, hSBA-MenW, and hSBA-MenY titers  $\geq 1:4$ ,  $\geq 1:8$ ,  $\geq 1:16$ ,  $\geq 1:32$ ,  $\geq 1:64$ , and  $\geq 1:128$  at Visit 2.
- hSBA GMTs for each of the ACWY test strains at Visit 2.

Immune response induced by 2 doses of MenABCWY compared to 1 dose of MenACWY-CRM arms in ACWY-naïve and ACWY-experienced subjects separately.

- Proportion of subjects with hSBA-MenA, hSBA-MenC, hSBA-MenW, and hSBA-MenY titers  $\geq 1:8$  (or LLOQ, whichever is higher) at Visit 4 in Groups 1 and 3 and at Visit 2 in Groups 2 and 4.
- Proportion of subjects with hSBA-MenA, hSBA-MenC, hSBA-MenW, and hSBA-MenY titers  $\geq 1:4$ ,  $\geq 1:8$ ,  $\geq 1:16$ ,  $\geq 1:32$ ,  $\geq 1:64$ , and  $\geq 1:128$  at Visit 4 in Groups 1 and 3 and Visit 2 in Groups 2 and 4.
- hSBA GMTs for each of the ACWY test strains at Visit 4 in Groups 1 and 3 and Visit 2 in Groups 2 and 4.

Immune response induced by 2 doses of MenABCWY compared to immune response induced by 2 doses of bivalent rLP2086 arms in ACWY-naïve and ACWY-experienced subjects combined.

- Proportion of subjects who achieve the 5 MenB endpoints 1 month after the second vaccination, which are defined for hSBA performed with each of the 4 primary test strains: PMB80 (A22), PMB2001 (A56), PMB2948 (B24), and PMB2707 (B44), as detailed below:
  - One of the 5 endpoints is the composite endpoint defined as the proportion of subjects achieving an hSBA titer  $\geq$  LLOQ (1:16 for A22 and 1:8 for A56, B24, and B44) for all 4 primary test strains combined, 1 month after the second vaccination.
  - Four of the endpoints are defined as the proportion of subjects achieving at least a 4-fold increase in hSBA titer from baseline to 1 month after the second vaccination for each of the 4 primary test strains.

- For subjects with a baseline hSBA titer below the LOD (ie, an hSBA titer of <1:4), a 4-fold response is defined as an hSBA titer of  $\geq 1:16$  or the LLOQ (whichever titer is higher).
- For subjects with a baseline hSBA titer of  $\geq$  LOD (ie, hSBA titer of  $\geq 1:4$ ) and < LLOQ, a 4-fold response is defined as an hSBA titer of  $\geq 4$  times the LLOQ.
- For subjects with a baseline hSBA of  $\geq$  LLOQ, a 4-fold response is defined as an hSBA titer of  $\geq 4$  times the baseline titer.
- Proportion of subjects with hSBA titers  $\geq$  LLOQ,  $\geq 1:4$ ,  $\geq 1:8$ ,  $\geq 1:16$ ,  $\geq 1:32$ ,  $\geq 1:64$ , and  $\geq 1:128$  for each of the 4 primary MenB test strains at Visit 4.
- hSBA GMTs for each of the 4 primary MenB test strains at Visit 4.

Immune response induced by MenABCWY compared to MenACWY-CRM and bivalent rLP2086 during Stage 1.

- Proportions of subjects with hSBA-MenA, hSBA-MenC, hSBA-MenW, and hSBA-MenY titers  $\geq 1:8$  (or LLOQ, whichever is higher) at Visits 1 and 3, in the ACWY-naïve and ACWY-experienced subjects separately.
- Proportions of subjects with hSBA-MenA, hSBA-MenC, hSBA-MenW, and hSBA-MenY titers  $\geq 1:4$ ,  $\geq 1:8$ ,  $\geq 1:16$ ,  $\geq 1:32$ ,  $\geq 1:64$ , and  $\geq 1:128$  at Visits 1 and 3, in the ACWY-naïve and ACWY-experienced subjects separately.
- hSBA GMTs for each of the ACWY test strains at Visits 1 and 3, in the ACWY-naïve and ACWY-experienced subjects separately.
- Proportions of subjects with hSBA titers  $\geq$  LLOQ,  $\geq 1:4$ ,  $\geq 1:8$ ,  $\geq 1:16$ ,  $\geq 1:32$ ,  $\geq 1:64$ , and  $\geq 1:128$  for each of the 4 primary MenB test strains at Visits 1 and 3, in the ACWY-naïve and ACWY-experienced subjects combined.
- hSBA GMTs for each of the 4 primary MenB test strains at Visits 1 and 3, in the ACWY-naïve and ACWY-experienced subjects combined.

Immune response induced by MenABCWY compared to MenACWY-CRM and bivalent rLP2086 at blood sampling time points prior to the booster vaccination (Stage 2).

- Proportions of subjects with hSBA-MenA, hSBA-MenC, hSBA-MenW, and hSBA-MenY titers  $\geq 1:8$  (or LLOQ, whichever is higher) at Visits 7, 8, 9, and 10, in the ACWY-naïve and ACWY-experienced subjects separately.

- Proportions of subjects with hSBA titers  $\geq$  LLOQ for each of the 4 primary MenB test strains at Visits 7, 8, 9, and 10, in the ACWY-naïve and ACWY-experienced subjects combined.

Immune response induced by MenABCWY 1 month after a booster vaccination in Groups 1 and 3.

- Proportions of subjects with hSBA-MenA, hSBA-MenC, hSBA-MenW, and hSBA-MenY titers  $\geq$ 1:8 (or LLOQ, whichever is higher) at Visit 11 in Groups 1 and 3 separately.
- Proportions of subjects with hSBA titers  $\geq$  LLOQ for each of the 4 primary MenB test strains at Visit 11 in Groups 1 and 3 combined.

Immune response induced by bivalent rLP2086 measured 1 month after the booster vaccination in Groups 2 and 4.

- Proportions of subjects with hSBA titers  $\geq$  LLOQ for each of the 4 primary MenB test strains at Visit 11 in Groups 2 and 4 combined.

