
 To describe the immune response induced by 2 doses of MenABCWY compared to the immune response induced by 1 dose of MenACWY-CRM, as measured by hSBA performed with ACWY test strains, in ACWY-naive and ACWY-experienced subjects separately. 	
 Proportions of subjects with hSBA-MenA, hSBA-MenC, hSBA-MenW, and hSBA-MenY titers \geq1:8 (or LLOQ, whichever is higher) at Visit 4 in Groups 1 and 3 and at Visit 2 in Groups 2 and 4. Proportions of subjects with hSBA-MenA, hSBA-MenC, hSBA-MenW, and hSBA-MenY titers \geq1:4, \geq1:8, \geq1:16, \geq1:32, \geq1:64, and \geq1:128 at Visit 4 in Groups 1 and 3 and Visit 2 in Groups 2 and 4. hSBA GMTs for each of the ACWY test strains at Visit 4 in Groups 1 and 3 and Visit 2 in Groups 2 and 4.

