3. STUDY DESIGN

This is a Phase 3, randomized, active-controlled, observer-blinded multicenter trial in which approximately 1590 subjects will be randomly assigned to receive either MenABCWY and placebo, or bivalent rLP2086 and MenACWY-CRM. All subjects will be naive to any meningococcal group B vaccine prior to enrollment.

Randomization will be stratified by prior vaccination history; approximately 795 ACWY-naive subjects and 795 ACWY-experienced (having received 1 prior dose of a vaccine containing 1 or more ACWY groups ≥ 4 years prior to the date of randomization) subjects will be enrolled.

Randomization will also be stratified by geographic region. Approximately 1320 subjects from US investigative sites and 270 subjects from ex-US countries will be randomized. Regional stratification will ensure sufficient population representation.

Enrollment targets will also be adjusted to achieve appropriate representation by age (subjects 10 to <18 years old and subjects 18 to <26 years old), age within ACWY strata, and ACWY strata within a geographic region. Additional details will be provided during pretrial assessment and site initiation visits.

The study will be conducted in 2 stages:

- Stage 1: from study entry (Visit 1) through Visit 6. See Table 1. A pilot cohort consisting of 10 subjects 18 to <26 years of age will first be enrolled at selected site(s). These pilot cohort subjects will be assigned to either Group 1 or 3, and therefore will receive MenABCWY at Vaccination 1. The sponsor will be unblinded to vaccine assignment for the pilot cohort. Seven (7) days after the last pilot cohort subject has received MenABCWY, 7-day electronic diary (e-diary) and AE data will be summarized for review by the sponsor’s independent review committee (IRC). No further enrollment will be permitted until review of these safety data is complete. If the IRC finds the safety data from the pilot cohort acceptable, enrollment will be opened to all ages and randomization groups, and pilot cohort subjects will proceed through the study. During Stage 1, the sponsor will be blinded to vaccine assignment beyond completion of pilot cohort enrollment (Section 5.4).

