- = 0, if not all 4 MenB primary strains have assay results  $\geq$  LLOQ.

In [Section 6.4](#), a supportive analysis is included describing different handling of missing values for the composite response.

For MenB-related endpoints, the 4-fold response in assay titers from baseline (Visit 1 prevaccination) to 1 month after the second vaccination (Visit 4) will be defined as follows:

- For subjects with a baseline hSBA titer < LOD or an hSBA titer of <1:4, a 4-fold response is defined as an hSBA titer of  $\geq 1:16$  or the LLOQ (whichever titer is higher).
- For subjects with a baseline hSBA titer of  $\geq$  LOD (ie, hSBA titer of  $\geq 1:4$ ) and < LLOQ, a 4-fold response is defined as an hSBA titer of  $\geq 4$  times the LLOQ.
- For subjects with a baseline hSBA of > LLOQ, a 4-fold response is defined as an hSBA titer of  $\geq 4$  times the baseline titer.

The 4-fold response variable for the 4 MenB primary strains will be computed as:

= •, if the assay result at baseline or specific time point is missing, indeterminate, or otherwise unavailable;

= 1, if the assay result meets 1 of the 3 definitions for a 4-fold response;

= 0, if the assay result does not meet 1 of the 3 definitions for a 4-fold response.

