**Table 19. Analysis for MenABCWY Immune Response Secondary Objectives**

Stage of Study	Objective	Randomized Groups	Analysis Time Point	Analysis Population(s)	Strain/Serogroup	Analysis Endpoint
Booster	ABCWY response after MenABCWY booster dose	1+3 and 2+4	Visits 4, 10, and 11 (post-Vaccination 2 blood draw, before booster vaccination, postbooster blood draw)	Booster evaluable immunogenicity	PMB80(A22) PMB2001(A56) PMB2948(B24) PMB2707(B44)	Subjects with hSBA titer $\geq$ LLOQ for each strain
		1 vs 3	Visits 4, 10, and 11 (post-Vaccination 2 blood draw, before booster vaccination, postbooster blood draw)	Booster evaluable immunogenicity	MenA MenC MenW MenY	Subjects with hSBA titer $\geq$ 1:8 (or LLOQ, whichever is higher) for each serogroup

Abbreviations: ACWY = ACWY = *Neisseria meningitidis* group A, C, W, Y; GMT = geometric mean titer; hSBA = serum bactericidal assay using human complement; LLOQ = lower limit of quantitation; MenA = *Neisseria meningitidis* serogroup A; MenB = *Neisseria meningitidis* serogroup B; MenC = *Neisseria meningitidis* serogroup C; MenW = *Neisseria meningitidis* serogroup W; MenY = *Neisseria meningitidis* serogroup Y.

- a. The hSBA titer  $\geq$ 1:8 (or LLOQ, whichever is higher) is identical to hSBA titer  $\geq$ 1:8 since LLOQs for the ACWY serogroups have all been confirmed to be 1:8.

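### The ACWY endpoint of a titer of at least 1:8 counts subjects already there before the dose, and no subject-level rate of rise is planned for A, C, W or Y

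*SAP*

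**What the plan says.** **Objectives.** Protocol Section 2 and SAP 2.1.3 word the ACWY aims as responses induced by vaccine. SAP 3.2.1 heads the 1-dose endpoints "Immune response induced by 1 dose of MenABCWY compared to 1 dose of MenACWY-CRM arms in ACWY-naïve and ACWY-experienced subjects separately". The 2-dose aim is "To describe the immune response induced by 2 doses of MenABCWY compared to the immune response induced by 1 dose of MenACWY-CRM", in naive and experienced subjects separately. The experienced stratum is defined as "ACWY-experienced (having received 1 prior dose of a vaccine containing 1 or more ACWY groups", given at least 4 years before randomization (Protocol Section 3).

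**Stage 1 ACWY endpoints** (SAP 3.2.1, Table 19).
- The proportion at or above 1:8 or the LLOQ, whichever is higher. The Table 19 footnote reduces this to 1:8, "since LLOQs for the ACWY serogroups have all been confirmed to be 1:8".
- Proportions at fixed cutoffs from 1:4 to 1:128.
- GMTs, for example "hSBA GMTs for each of the ACWY test strains at Visit 2".
- The same three summaries across Visits 1, 2, 3 and 4 in one row of Table 19, plus reverse cumulative distribution curves at Visits 1, 2 and 4 (SAP 6.2.1.2).

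**Rise from baseline.** SAP 5.2.1.2 limits its scope: "For MenB-related endpoints, the 4-fold response in assay titers from baseline (Visit 1 prevaccination) to 1 month after the second vaccination (Visit 4"). It continues: "The 4-fold response variable for the 4 MenB primary strains will be computed as". ACWY fold-rises appear once, in SAP 6.4, as scatterplots with correlations for the booster and optionally for Doses 1 and 2.

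**Booster ACWY reporting.** Groups 1 and 3 have the 1:8 proportion (Table 19) and GMTs (Table 21). Groups 2 and 4 have the 1:8 proportion only (Table 21). SAP 2.1.5 and 3.3.1 state that the post-booster proportions at fixed cutoffs will not be reported.

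**The concern.** MenB, where every subject enters vaccine-naive, gets a baseline-corrected responder definition. The serogroups for which half of the planned trial (795 of 1590) has had a prior dose do not. An experienced subject with a Visit 1 titer of 1:8 or more and no rise is counted at Visits 2 and 4 exactly like a subject who responded. By Visit 10 the same applies to all four groups: under Protocol Table 3, Groups 1 and 3 have had two MenABCWY doses and Groups 2 and 4 one MenACWY-CRM dose.

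What is at stake is interpretation. Two high and similar percentages in Groups 3 and 4 could be taken as similar vaccine responses when part of each reflects earlier immunity.

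**Working it through.** There is no plan figure to reproduce. The documents give no power, margin or sample size for any ACWY endpoint and no Visit 1 or Visit 10 ACWY seropositivity. The check is therefore the reading above plus two illustrations with stated assumptions.

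**1. Dilution of a between-arm difference (Stage 1, Group 3 versus Group 4).** Let b be the share at or above 1:8 before the dose, equal in both arms by stratified randomization. Let r be the proportion of the rest who reach 1:8. Assume those already there stay there. Then

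observed proportion = b + (1 − b) × r, and observed difference = (1 − b) × (difference in r).

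With assumed r of 90% and 80%:

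| b (assumed) | r = 90% | r = 80% | Observed gap |
|---|---|---|---|
| 0 | 90% | 80% | 10 points |
| 0.2 | 0.2 + 0.8 × 0.9 = 92% | 0.2 + 0.8 × 0.8 = 84% | 8 points |
| 0.5 | 0.5 + 0.5 × 0.9 = 95% | 0.5 + 0.5 × 0.8 = 90% | 5 points |
| 0.8 | 0.8 + 0.2 × 0.9 = 98% | 0.8 + 0.2 × 0.8 = 96% | 2 points |

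This formula describes the 1:8 cutoff only.

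**2. What each measure records.** Titers were simulated on the log2 scale: baseline SD 2, mean set to give b, post-dose rise with SD 1 (or no rise), titers rounded down to a doubling dilution. The MenB three-tier rule was applied with the ACWY values LOD 1:4 and LLOQ 1:8 (SAP Table 16). A baseline below 1:4 needs at least 1:16, a baseline from 1:4 to below 1:8 needs at least 1:32, and a baseline of 1:8 or more needs four times baseline.

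| b (assumed) | No rise: ≥1:8 | No rise: 4-fold | Mean 4-fold rise: ≥1:8 | Mean 4-fold rise: 4-fold |
|---|---|---|---|---|
| 0.2 | 20% | 0% | 56% | 26% |
| 0.4 | 40% | 0% | 75% | 40% |
| 0.6 | 60% | 0% | 87% | 51% |
| 0.8 | 80% | 0% | 95% | 60% |

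A vaccine that raises no titer scores b on the 1:8 endpoint and zero on the 4-fold rule. The 4-fold rate also moves with b, so it complements the 1:8 proportion and cannot replace it.

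**The case against.** The case for leaving the plan alone is substantial.

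- **Baseline is not ignored.** Visit 1 proportions and GMTs sit beside the post-dose values in Table 19, and the reverse cumulative curves show the whole titer distribution before and after. For subjects with both titers, the ratio of the two GMTs is the geometric mean fold rise. This stands for Stage 1. It gives an average, but not a subject-level rate with a CI.
- **Higher cutoffs relieve the ceiling.** True in Stage 1. After the booster they are dropped, although the Visit 10 proportion at 1:8 is tabulated with Visit 11.
- **A fixed titer has a rationale.** Protocol 1.2.3 gives an hSBA titer of 1:4 as the MenC correlate of protection and notes its customary extension to A, W and Y. The 1:8 proportion therefore deserves to stay.
- **Nothing is tested.** Protocol 9.2.2 calls these analyses descriptive. That limits the consequence to interpretation.
- **SAP 6.4 already relates pre-booster titer to fold-rise.** It does so through plots and correlations, and wavers between analyses that may be performed and plots that will be provided. It defines no responder and gives no proportion or interval.

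A reader might infer that the endpoint favors one vaccine. In Stage 1 the documents do not support this: randomization is stratified by ACWY history and the comparison is within stratum (SAP 6.2.1.2), so prior immunity should be balanced. A reader might also take the 1:8 proportion as the main ACWY endpoint. The plan gives no ACWY endpoint that rank in Stage 1; it is only the first listed, and the only secondary ACWY endpoint carried into Stage 2.

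**Conclusion.** The point holds as a gap in description. In experienced subjects in Stage 1, and in every group at the booster, the 1:8 proportion shows titer reached and not response induced. It attenuates a Stage 1 between-arm difference by the factor (1 − b). The size is unknown because b is not in the documents; a 10-point gap falling to between 8 and 2 points for b from 0.2 to 0.8 is illustrative and rests on assumed response rates. Half the trial is an upper bound for A, W and Y, since recipients of monovalent C vaccine are excluded from those assessments (SAP 6.2.1.2).

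The gap is modest in Stage 1 and clearest after the booster. There Groups 2 and 4 have one ACWY summary, and Tables 19 and 21 pair groups across strata (1 with 3, 2 with 4). The pre-booster share at 1:8 may differ between those pairs, and randomization does not balance it. The documents do not support concluding that ACWY baseline is left unreported or that the 1:8 threshold is the wrong measure.

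**What to change.** Keep the 1:8 proportion as the titer-threshold measure. Add, for each of A, C, W and Y, a supplementary descriptive endpoint: the proportion with a 4-fold rise under the existing three-tier rule (LOD 1:4, LLOQ 1:8), with Clopper-Pearson CI, by ACWY stratum.

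- **Booster:** Visit 10 to Visit 11 in all four groups, written into SAP 5.2.1.2 and Tables 19 and 21 before the final Stage 2 analysis, and preferably before the Visit 11 reporting event in SAP 7.1. SAP 3.4 already names Visit 10 as the Stage 2 baseline.
- **Stage 1:** Visit 1 to Visit 2 in all groups, and Visit 1 to Visit 4 in Groups 1 and 3 set against Visit 2 in Groups 2 and 4. Label this post hoc, because SAP 3.5.2.2 refers to Stage 1 reporting as done.
- **Wording:** take the third tier from SAP 3.1.1 (baseline at or above LLOQ). SAP 5.2.1.2 writes it as strictly above, which leaves a baseline of exactly 1:8 unclassified.

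The cost is SAP text and a few tables reusing the MenB derivation; no new blood draws or assays are needed. The limits are that the Stage 1 results can only be post hoc, and that the 4-fold rate itself depends on baseline titer, so it should be read beside the 1:8 proportion and the GMTs.
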